The date of the first dose of cabozantinib is defined as Baseline (Day 1, Visit 2). In both cohorts, subjects can receive study treatment up to the end of the study, defined as 18 months after the last subject included in the study started cabozantinib treatment, but subjects may terminate treatment earlier due to reasons such as disease progression, unacceptable toxicity or withdrawal of consent.

Efficacy evaluations will be performed as described in Section 1.3.2.1 (see [Table 2](#) for schedule of assessments). These include radiographic tumour assessments which will be blindly reviewed by a central independent radiology committee (IRC) to evaluate efficacy endpoints (Sections 3.1.1 and 3.1.2).

[figure not shown]
Safety assessments will start on the date of the Screening visit and will be continued throughout the study as described in Section 1.3.2.2 (see [Table 2](#) for schedule of assessments). Unscheduled safety evaluations are allowed at any time throughout the study.

Subjects who discontinue study treatment with cabozantinib due to disease progression or unacceptable toxicity will be invited to attend the End of Study Treatment visit (30 days to 45 days after the last dose of cabozantinib). Subjects who prematurely stop the study will be invited to attend the Early Study Withdrawal visit.

SAP Final: Version 6.0: 17 August 2023

Post-treatment Follow-up Period: Subjects who discontinue study treatment will be contacted during the Post-treatment Follow-up visits every 12 weeks ± 15 days to assess survival status and collect information about subsequent anti-cancer therapy. During the follow-up period, any serious AEs (SAEs) that occur more than 30 days after the date of the last cabozantinib dose, assessed as related to study treatment or study procedures will also be collected and followed until resolution or stability according to the Investigator. These assessments will be continued until the subject expires or until the end of the study (18 months after the last subject included in the study started cabozantinib treatment), whichever occurs first. Every effort will be made to collect these protocol-specific evaluations unless consent to participate in the study is withdrawn.

Figure 1 Study Design

Abbreviations: CPI = Checkpoint inhibitor; PO = Orally; q.d. = Once daily; VEGF = Vascular endothelial growth factor

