Pregnancy itself is not regarded as an AE unless there is a suspicion that the IMP has interfered with a contraceptive method. If pregnancy occurs during the study, the outcome of the pregnancy will be collected and it will be necessary to discontinue administration of the IMP. Information regarding pregnancies must be collected on the AE page of the electronic case report form (eCRF).

Clinical Laboratory Tests

Blood and urine samples will be collected at the frequency indicated in [Table 2](#) and as detailed below for the evaluation of haematology, blood biochemistry, urinalysis, pregnancy tests and other clinical laboratory tests as safety measurements.

All laboratory tests to establish eligibility must be done within 15 days prior to baseline. Then, Haematology, blood biochemistry and urinalysis will be collected at Baseline, Week 2, Week 4, Week 8 and every 4 weeks until the End of Study Treatment visit or Early Study Withdrawal visit. Thyroid function test will be collected at Baseline and every 4 weeks.

A β -human chorionic gonadotrophin (HCG) serum test and/or an HCG urine test will be performed for all female subjects of childbearing potential within 7 days prior to the baseline visit and at every visit thereafter up to the End of Study Treatment or Early Study Withdrawal visit. Any subject becoming pregnant during the study will be withdrawn from the study.

SAP Final: Version 6.0: 17 August 2023

A list of all laboratory analyses that will be measured in this study is provided in [Table 1](#).

All laboratory analyses will be performed and analysed by the local laboratory, including samples that are obtained at unscheduled visits whenever possible. All local laboratory results and normal ranges will be recorded on the eCRF and provided by the Investigator.

Table 1 Laboratory Assessments

| | | |
|---|---|--|

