| Haematology 
- White blood cells with differential count (absolute neutrophil count [ANC]), basophils, eosinophils, lymphocytes and monocytes- Haematocrit- Platelet count- Red blood cell count- Haemoglobin | Blood Chemistry 
- Albumin- Total alkaline phosphatase (ALP)- Alanine aminotransferase (ALT)- Aspartate aminotransferase (AST)- Blood urea nitrogen (BUN)- Chloride- Creatinine (estimation of creatinine clearance by Cockcroft and Gault)- γ-glutamyl transpeptidase (GGT)- Glucose- Potassium- Sodium- Corrected calcium- Total bilirubin (conjugated and unconjugated if total bilirubin is elevated)- Total protein | Pregnancy Blood/Urine Test 
- β-human chorionic gonadotrophin (β-HCG) Urinalysis (Dipstick or Routine)^a 
- pH- Protein- Glucose- Blood Microscopic Urine Examination^a 
- At the discretion of the Investigator based on results or routine urinalysis or as clinically indicated Urine Chemistry (at the discretion of the Investigator and based on results of routine urinalysis or as clinically indicated) ^a 
- 24-hour urine protein or urine protein-to-creatinine ratio (UPCR) |
| Coagulation 
- Prothrombin time/International normalised ratio (INR)- Partial thromboplastin time (PTT) | | |
| Thyroid function 
- Thyroid-stimulating hormone (TSH)- Free Thyroxine 4 (FT4) | | |

^a Fresh urine samples will be collected to perform these assessments.

Vital Signs

Vital signs (BP [blood pressure] and heart rate) will be assessed as indicated in [Table 2](#) as safety measures.

Vital signs will be measured at the Screening visit, Baseline, Week 2, Week 4, Week 8 and every 4 weeks until the End of Study Treatment visit or Early Study Withdrawal visit.

These assessments will be conducted with an automated device so that measurements are independent of the observer. Measurements of BP and heart rate will be performed after a 5-minute rest in sitting position and after standing up for 1 minute. Absolute values and change from Baseline will be analysed. Any clinically significant abnormalities as per investigator assessment in the vital signs will be reported as an AE.

SAP Final: Version 6.0: 17 August 2023

Electrocardiography

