Concordance in Overall Response Rate and BOR assessed by independent central review and by Investigator will be described using shift tables for each cohort separately (Tables 14.2.4.3 and 14.2.4.4). The concordance will be presented for the subjects with assessments in both populations i.e. from both IRC and investigator assessments.

General censoring rules for the analysis of PFS are described in [Appendix 1 \(4\)](#).

Additional supportive analyses of PFS below will be performed using alternative event definitions and censoring schemes to account for partial or completely missing assessments, address bias due to tumour assessment timing, evaluate the impact of potentially informative censoring, and to address potential discrepancies between the

SAP Final: Version 6.0: 17 August 2023

documentation of progression per the Investigator and per the independent central review. This is applicable for PFS only. These additional supportive analyses will be performed on the Efficacy population only.

- The primary PFS analyses described above will be repeated with the same general censoring rules, except that the progression or death will be considered a PFS event regardless of when it occurs during the study i.e. the event will be considered a PFS event even if the subjects missed two or more scheduled tumour assessment prior this event and/or even if the subjects received NPACT prior the event (Table 14.2.2.4, Figure 14.2.2.5, Table 14.2.5.5 and Figure 14.2.5.6);
- The primary PFS analyses described above will be repeated with the same general censoring rules, except that non-radiological disease progression will also be considered a PFS event (Table 14.2.2.6, Figure 14.2.2.7, Table 14.2.5.7 and Figure 14.2.5.8).
- The primary PFS analyses described above will be repeated with the same general censoring rules, with additional censoring at last tumour assessment prior to treatment discontinuation for subjects who discontinued study treatment due to reasons other than PD or death (Table 14.2.2.8, Figure 14.2.2.9, Table 14.2.5.9 and Figure 14.2.5.10).

3.2.2 *Safety*

All safety data will be included in the subject data listings. Analyses and summary tables will be based upon the safety population as defined in Section 2.2 and will be presented in each cohort separately and overall.

3.2.2.1 *Adverse events*

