All text fields must be left justified and numeric or numeric with some text specification (e.g.: not done, unknown, <4.5, ...) must be decimal justified. Dates will be presented in the format [ddmmmyyyy] and times in the format [hh:mm] in 24-hour time format.

3.2.14 *Pooling of Centres*

It is not planned to perform a subgroup analysis on individual or groups of centres.

3.2.15 *Interim analysis*

An interim and purely descriptive analysis will be conducted when 80% of subjects (i.e. 59 subjects) of the cohort A will be treated for at least 3 months. Both cohorts will be analysed at this cut-off date.

The aim of this interim analysis is to describe the baseline characteristics, demographics, ORR as assessed by the Investigator at 3 months and any further efficacy parameters measured at the Month 3 visit. A subset of Tables, Figures and Listings (TFLs) will be produced for this interim analysis. The results of this interim analysis will not have any impact on the study conduct.

A final analysis based on the primary endpoint (ORR) will be performed 12 months after the last subject received the first cabozantinib administration, i.e. as soon as all subjects have discontinued study treatment or at the latest 12 months after the last subject received the first cabozantinib administration whichever occur first. A cut-off will be performed considering the date when last subject received the first cabozantinib administration plus 12 months.

A follow-up analysis based on OS will be conducted 18 months after the last subject received the first cabozantinib administration.

SAP Final: Version 6.0: 17 August 2023

The statistical testing will only be carried out at the final analysis.

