Appendix 4: List of Tables, Figures and Listings (TFLs) for Follow-Up Analysis

| | |
|-----------------|--|
| Table 14.1.2 | Subject Disposition by Visit (All subjects) |
| Table 14.1.4 | Sample Size of Analysis Populations by Country and Site (All subjects) |
| Table 14.1.5 | Study Exposure (Safety Population) |
| Table 14.1.6 | Study Drug Exposure (Safety Population) |
| Table 14.1.7 | Study Drug Dose Reduction, Interruption and Escalation (Safety Population) |
| Table 14.1.8 | Subject Disposition and Withdrawals (Screened Population) |
| Table 14.1.17 | Compliance (Safety Population) |
| Table 14.1.19 | Concomitant Medications (Safety Population) |
| Table 14.1.21 | Concomitant Non-Drug Therapies (Safety Population) |
| Table 14.1.25 | Concomitant Surgical Procedures (Safety Population) |
| Table 14.1.26 | Subsequent Anticancer Therapies (Safety Population) |
| Table 14.1.27 | Subsequent Anticancer Radiotherapies (Safety Subjects) |
| Table 14.1.28 | Subsequent Anticancer Surgical Procedures (Safety Population) |
| Table 14.2.3.1 | Overall Survival (OS) (Efficacy Population - Investigator) |
| Table 14.2.3.2 | Overall Survival (OS) (Per Protocol Population - Investigator) |
| Figure 14.2.3.3 | Kaplan-Meier Plot of Overall Survival (OS) (Efficacy Population - Investigator) |
| Table 14.3.1.1 | Overview of Adverse Events (Safety Population) |
| Table 14.3.1.2 | Summary of Treatment-Emergent Adverse Events by System Organ Class and Preferred Term (Safety Population) |
| Table 14.3.1.3 | Summary of Treatment-Emergent Adverse Events with Incidence Rate $\geq 10\%$ by System Organ Class and Preferred Term (Safety Population) |
| Table 14.3.1.4 | Summary of Treatment-Emergent Adverse Events with CTCAE Severity Grade 3 or 4 by System Organ Class and Preferred Term (Safety Population) |
| Table 14.3.1.5 | Time to onset for Treatment-Emergent Adverse Events with CTCAE Severity Grade 3 or 4 (Safety Population) |
| Figure 14.3.1.6 | Kaplan-Meier Plot of time to onset for Treatment-Emergent Adverse Events with CTCAE Severity Grade 3 or 4 (Safety Population) |
| Table 14.3.1.7 | Summary of Treatment-Emergent Adverse Events by CTCAE Severity Grade and System Organ Class and Preferred Term (Safety Population) |
| Table 14.3.1.8 | Summary of Treatment-Emergent Adverse Events by Causality and System Organ Class and Preferred Term (Safety Population) |

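### Laboratory, vital-sign, ECG, weight and ECOG values recorded after the 12-month cut-off have no planned table or listing, although the SAP says all safety data will be listed

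*SAP*

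**What the plan says.** SAP 1.2 lets treatment run past the final analysis: "subjects can receive study treatment up to the end of the study, defined as 18 months after the last subject included in the study" (counted from that patient's first dose). SAP 1.3.2.2 keeps safety measurements going for as long as a patient is treated. For laboratory tests: "Haematology, blood biochemistry and urinalysis will be collected at Baseline, Week 2, Week 4, Week 8 and every 4 weeks". For vital signs: "Baseline, Week 2, Week 4, Week 8 and every 4 weeks until the End of Study Treatment visit or Early Study Withdrawal visit". Physical examination, which includes weight and performance status, follows the same 4-weekly pattern, and ECG is every 12 weeks. None of these schedules stops at month 12.

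SAP 3.2.15 sets two analysis dates. For the final analysis: "A cut-off will be performed considering the date when last subject received the first cabozantinib administration plus 12 months". Then: "A follow-up analysis based on OS will be conducted 18 months after the last subject received the first cabozantinib administration". Appendix 3 lists the outputs of the former, and those of the latter stand under the heading "Appendix 4: List of Tables, Figures and Listings (TFLs) for Follow-Up Analysis".

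On reporting, SAP 3.2.2 says: "All safety data will be included in the subject data listings". Protocol 11.4.4 makes the same commitment and adds summary statistics for vital signs, ECG variables and laboratory tests at each assessment. SAP 3.1.3 names all of these as safety endpoints. Protocol 17.2 plans a report addendum at 18 months that includes analysis of the follow-up data.

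**The concern.** Six months of scheduled safety measurements fall between the two analysis dates, and Appendix 4 seems to have no place for them. If so, the study report would update adverse-event counts and drug exposure to 18 months, while the worst laboratory grades, vital-sign threshold counts, ECG results, ECOG shifts and weight-loss classes stayed at 12 months. The two halves of the safety section would describe different exposure. The missing values would all come from the patients treated longest or latest, where one would look for slow changes in thyroid function, renal function, blood pressure or weight.

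**Working it through.** The plan gives no figure to reproduce, so the check compares the output lists and then sizes the gap.

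**Step 1. Compare the lists.**

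| Output | Appendix 3 (12 months) | Appendix 4 (18 months) |
|---|---|---|
| Laboratory tables 14.3.4.x | yes | no |
| Vital-sign tables 14.3.5.x | yes | no |
| ECG tables 14.3.6.x | yes | no |
| ECOG and weight tables 14.3.7.x | yes | no |
| Laboratory listings 16.2.8.x | yes | no |
| Vital-sign, ECG, examination and ECOG/weight listings 16.2.9.x | yes | no |
| Adverse events and deaths, 14.3.1.x, 14.3.2.x and 16.2.7.x | yes | yes |
| Drug exposure 14.1.6 and dates of visits 16.2.1.3 | yes | yes |
| Overall survival 14.2.3.x | no | yes |

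Appendix 2 (interim) contains none of the missing outputs, and no analysis is planned after 18 months. In Appendix 4 the tables end at 14.3.2.22 and the next entry is Listing 16.1.6, so the absent tables are not text lost in reading the file. The listings end at 16.2.7.9, which is also the end of the document, but they match the table list in stopping after adverse events.

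**Step 2. Look for a declared exception.** SAP Section 5 records five changes from the protocol, and this is not one of them. The SAP history of changes says only that an appendix for the follow-up analysis was added and its populations later updated.

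**Step 3. Measurements per patient in the gap.** Six months is 6 × 30.4375 = 182.6 days. That gives 182.6/28 = 6.5, or about six 4-weekly visits, and 182.6/84 = 2.2, or about two ECGs, for a patient treated throughout the window.

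**Step 4. Patients affected.** Inputs from the documents: mean time on treatment 8 months (SAP 1.2.2) and about 114 patients (SAP 1.2). Assumptions: exponential time on treatment with mean m, and uniform accrual over A months. The fraction still on drug at the cut-off is

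(m/A) × [exp(−12/m) − exp(−(12+A)/m)].

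With m = 8:
- A = 18: (8/18) × (0.2231 − 0.0235) = 0.0887, times 114 = 10.1
- A = 24: (8/24) × (0.2231 − 0.0111) = 0.0707, times 114 = 8.1
- A = 30: (8/30) × (0.2231 − 0.0052) = 0.0581, times 114 = 6.6

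Varying the mean over the same accrual range gives 3.1 to 4.9 patients for m = 6, 10.9 to 15.9 for m = 10 and 15.4 to 21.7 for m = 12.

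**Step 5. Exposure in the gap for m = 8.** Each patient still on drug contributes on average 8 × [1 − exp(−6/8)] = 8 × 0.5276 = 4.22 months. For 6.6 to 10.1 patients that is about 28 to 43 patient-months, or 3% to 5% of 114 × 8 = 912.

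**The case against.** The strongest reply is that the narrow scope is deliberate. Both documents describe the 18-month analysis as based on OS. Progression-free survival, duration of response, tumour size and the symptom questionnaire are not rerun either, and no sentence promises laboratory or ECG tables at 18 months. This has force for the tables: apart from the protocol's general promise of summaries at each assessment, rerunning them is a matter of consistency. It does not answer the listings point, because the commitment to list all safety data is unqualified.

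A reader might infer that late safety changes are lost altogether. The documents do not support that. SAP 1.3.2.2 makes a laboratory abnormality an adverse event if it alters dosing, needs intervention or evaluation, or is judged clinically significant. Clinically significant vital-sign, ECG and examination findings are also recorded as adverse events. Appendix 4 reruns the Grade 3 or 4 tables, the table of adverse events related to laboratory tests (14.3.1.12) and the tables of events of special interest, which include renal failure and hepatotoxicity. A reader might also infer that the follow-up analysis repeats only adverse-event outputs. It does not: disposition, exposure, dose changes, compliance and concomitant therapies are repeated, and subsequent therapies and overall survival are added.

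Finally, the loss is conditional. SAP 3.2.15 allows for all patients having stopped treatment before the 12-month date. In that case little or nothing would be missing; at most, some End of Study Treatment visits, held 30 to 45 days after the last dose, could fall after the cut-off.

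**Conclusion.** The point stands in a limited form. Followed as written, the plan leaves laboratory, vital-sign, ECG, weight and ECOG values after the 12-month cut-off without any table or listing. That contradicts SAP 3.2.2 and Protocol 11.4.4, and the departure is not declared. What goes unreported is the measured values and what is derived from them: CTCAE laboratory grades and shifts, potentially clinically significant vital-sign values, ECG intervals and interpretations, ECOG shifts and weight-loss classes.

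The size is about 7 to 10 of 114 patients at the stated 8-month mean, about 3 to 22 for means of 6 to 12 months, and close to none if treatment had ended by the cut-off. These counts rest on the assumed exponential shape and uniform accrual. They also use the planned 114, whereas SAP Section 5 says cohort A exceeds its target of 74. The primary endpoint and its test are unaffected, so this is a minor point about complete and consistent safety reporting.

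**What to change.** Add Listings 16.2.8.1.1 to 16.2.8.1.9, 16.2.9.1.1, 16.2.9.1.2, 16.2.9.2, 16.2.9.3 and 16.2.9.4 to SAP Appendix 4, on data to the end of the study. This alone removes the contradiction on listings.

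Also rerun the cumulative summaries so that they cover the same exposure as the updated adverse-event tables: 14.3.4.2.x (laboratory grade and abnormality shifts), 14.3.4.4.x (urinalysis, 24-hour protein and UPCR), 14.3.5.2 (vital-sign thresholds), 14.3.6.1 and 14.3.6.3 (ECG), 14.3.7.1 (ECOG) and 14.3.7.3 (weight loss). If the sponsor prefers the narrower scope, SAP Section 5 should state and justify it, and the sentence in 3.2.2 should be qualified.

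The cost is a rerun of programs already specified for the final analysis, with no new data collection. The one complication is the laboratory normalisation in SAP 3.2.2.2. Later values must be normalised too, and the reference site, defined as the one with the most blood samples, could change. Keeping the reference site used at the final analysis would avoid restating earlier values.
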